4.2 Inclusion Criteria

Each subject must meet the following criteria to be enrolled in this study:

1. Be at least 18 years of age.
2. Have stage 3 or 4 CKD (eGFR of ≥ 15 to <60 mL/min/1.73m² using the Modification of Diet in Renal Disease equation).
3. Be without any disease state or physical condition that might impair evaluation of safety and efficacy or which, in the Investigator's opinion, would interfere with study participation, including:
 - a. Serum albumin ≤ 3.0 g/dL;
 - b. Serum transaminase (alanine transaminase, glutamic pyruvic transaminase, aspartate aminotransferase or glutamic oxaloacetic transaminase) > 2.5 times the upper limit of normal at screening; and,
 - c. Urinary albumin excretion >3000 μ g/mg creatinine.
4. Exhibit during the initial Screening Visit:
 - a. Plasma iPTH ≥ 65 pg/mL and <400 pg/mL if receiving calcitriol or other 1 α -hydroxylated vitamin D analog (paricalcitol or doxercalciferol); or
 - b. Plasma iPTH ≥ 85 pg/mL and <500 pg/mL if not receiving calcitriol or other 1 α -hydroxylated vitamin D analog;
 - c. Serum total 25-hydroxyvitamin D <30 ng/mL, unless taking vitamin D supplementation (including multivitamins and fish oil); and,
 - d. If taking calcitriol or another 1 α -hydroxylated vitamin D analog, subjects must forgo treatment with these non-study agents for the duration of the study and undergo a 4-week washout period and meet inclusion criterion 5.
 - e. For subjects who are taking vitamin D supplementation (including multivitamins or fish oil), they must forgo treatment with these non-study agents for the duration of the study. If the serum 25-hydroxyvitamin D level is <30 ng/mL, there is no need for the subjects to complete a washout period as a result of vitamin D supplementation. If, however, serum 25-hydroxyvitamin D level is ≥ 30 ng/mL, the subjects must undergo a 4-week washout period and meet inclusion criterion 5. If at the end of 4 weeks of washout, the 25 hydroxyvitamin D level is still ≥ 30 ng/mL, the washout may be extended by up to another four weeks for a total of 8 weeks.
5. Exhibit after the washout period (if required):
 - a. Plasma iPTH ≥ 85 pg/mL and <500 pg/mL;

- b. Corrected serum calcium <9.8 mg/dL; (corrected for serum albumin)
- c. Serum total 25-hydroxyvitamin D <30 ng/mL; and,
- d. Serum phosphorus <5.5 mg/dL.
6. If taking more than 1,500 mg/day of elemental calcium, reduce calcium use (to approximately 1,000 to \leq 1,500 mg/day) for the duration of the study.

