4.3 Exclusion Criteria

Subjects who meet any of the following criteria will be excluded from the study:

1. History of or planned kidney transplant or parathyroidectomy.
2. History (prior 3 months) of corrected serum calcium \geq 9.8 mg/dL or serum phosphorus \geq 5.5 mg/dL if not receiving calcitriol or other 1 α -hydroxylated vitamin D analog.
3. Need for phosphate binders to maintain the serum phosphate < 5.5 mg/dL or use of phosphate binders within 4 weeks prior to screening.
4. Use of calcimimetic therapy (cinacalcet or etelcalcetide) within 12 weeks of screening.
5. Receipt of bisphosphonate therapy or other bone modifying treatment within 6 months prior to enrollment.
6. Known previous or concomitant serious illness or medical condition, such as malignancy, human immunodeficiency virus, significant gastrointestinal or hepatic disease, intestinal malabsorption disorder, hepatitis or cardiovascular event that in the opinion of the Investigator may worsen or reduce life expectancy, and/or interfere with participation in the study.
7. History of neurological/psychiatric disorder, including psychotic disorder or dementia, or any reason which, in the opinion of the Investigator makes adherence to a treatment or follow-up schedule unlikely.
8. Known or suspected hypersensitivity to any of the constituents of the study drugs.
9. Currently participating in, or has participated in, an interventional/investigational study within 30 days prior to study screening.

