5.4 Method of Assigning Subjects to Treatment Groups

After signing the ICF, prior to any study-related activities, each subject will be assigned a unique 7 digit subject identification number which will be retained throughout the study and that will be unique across all sites. The 7 digit subject identification number (SSSNNNN) will consist of a 3-digit site number (SSS) and a 4-digit subject number (NNNN) at the applicable clinical site. Should a subject be withdrawn from the study, that subject's 7 digit identification number will not be reassigned.

Randomization will be accomplished in blocks of 4 subjects in a 1:1:1:1 ratio with subjects being assigned to treatment with CTAP101 Capsules, IR calcifediol, high-dose cholecalciferol or paricalcitol plus low-dose cholecalciferol. Randomization will occur during Visit 4 provided that each subject is deemed eligible for enrollment based, in part, on laboratory assessments obtained at the preceding visit (Visit 1). Laboratory assessments obtained at Visits 2-3 will not be considered in the determination of enrollment eligibility.

In the event that a significant difference in mean baseline body weight among subjects by treatment group emerges as enrollment progresses, the randomization scheme (described immediately above) will be suspended and subjects will be assigned to a specific treatment group using the following alternative procedure:

Step 1: Calculate the mean body weight for subjects who have been previously entered into the treatment period, in aggregate and by treatment group.

Step 2: Compare the subject's body weight (measured at Visit 1) with the current mean body weight of all subjects who have previously been entered into the treatment period. If the subject's weight is equal to or higher than the current mean body weight of all previously treated subjects, then assign the subject to a treatment group (which still has less than 20 subjects) having the lowest mean body weight. If the subject's weight is lower than the current mean body weight of all previously treated subjects, then assign the subject to a treatment group (which still has less than 20 subjects) having the highest mean body weight.

Step 3 (if needed): If a subject cannot be assigned to a treatment group according to Step 2 (above) and there are fewer than 80 subjects assigned to treatment, then assign the subject to a treatment group (which still has less than 20 subjects) with the most similar mean body weight.

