9.3 Randomization

Each subject will be assigned a unique 7 digit subject identification number which will be retained throughout the study and that will be unique across all sites. The 7 digit subject identification number (SSSNNNN) will consist of a 3-digit site number (SSS) and a 4-digit subject number (NNNN) at the applicable clinical site. Should a subject be withdrawn from the study, that subject's 7 digit identification number will not be reassigned.

Randomization will be accomplished in blocks of 4 subjects in a 1:1:1:1 ratio with subjects being assigned to treatment with CTAP101 Capsules, IR calcifediol, high-dose cholecalciferol or paricalcitol plus low-dose cholecalciferol. Randomization will occur during Visit 4 provided that each subject is deemed eligible for enrollment based, in part, on laboratory assessments obtained at two preceding visits (Visits 1 and 2). Laboratory assessments obtained at Visit 3 will not be considered in the determination of enrollment eligibility. In the event that the treatment groups become unbalanced for mean baseline body weight as enrollment progresses, the randomization scheme (described immediately above) will be suspended and subjects will be assigned to treatment groups by the following alternative procedure:

Step 1: Calculate the mean body weight for subjects who have been previously entered into the treatment period, in aggregate and by treatment group.

Step 2: Compare the subject's body weight (measured at Visit 1) with the current mean body weight of all subjects who have previously been entered into the treatment period. If the subject's weight is equal to or higher than the current mean body weight of all previously treated subjects, then assign the subject to a treatment group (which still has less than 20 subjects) having the lowest mean body weight. If the subject's weight is lower than the current mean body weight of all previously treated subjects, then assign the subject to a treatment group (which still has less than 20 subjects) having the highest mean body weight.

Step 3 (if needed): If a subject cannot be assigned to a treatment group according to Step 2 (above) and there are fewer than 80 subjects assigned to treatment, then assign the subject to a treatment group (which still has less than 20 subjects) with the most similar mean body weight.

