### 3 STUDY DESIGN

#### 3.1 Number of Subjects

Approximately 160 subjects will be screened to enroll approximately 80 eligible subjects with approximately 20 subjects per treatment arm. After signing the informed consent form, prior to any study-related activities, each subject will be assigned a unique 7-digit subject identification number (SSSNNNN) which will be retained throughout the study and that will be unique across all sites. The number will consist of a 3-digit site number (SSS), followed by a 4-digit subject number (NNNN) at the applicable clinical site. Should a subject be withdrawn from the study, that subject's number will not be reassigned.

Randomization will be accomplished in blocks of 4 subjects in a 1:1:1:1 ratio, with subjects assigned to treatment with either CTAP101 Capsules, IR calcifediol, high-dose cholecalciferol, or paricalcitol plus low-dose cholecalciferol. Randomization will occur on Day 1 (Visit 4) provided that each subject is deemed eligible for enrollment based, in part, on laboratory assessments obtained at screening (Days -42 to -36, Visit 1). Laboratory assessments obtained at Days -7 to -1 (Visits 2-3) will not be considered in the determination of enrollment eligibility.

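### Protocol 5.4 and SAP 3.1 bar Visit 2 labs from eligibility while Protocol 9.3 uses them; under the bar, washout subjects have no visible usable draw for the post-washout calcium and phosphorus limits

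*Protocol*

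**What the plan says.** Three current sections govern the same randomisation step.

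- Protocol 5.4 rests eligibility, in part, on "laboratory assessments obtained at the preceding visit (Visit 1") and adds "Laboratory assessments obtained at Visits 2-3 will not be considered in the determination of enrollment eligibility".
- SAP 3.1 follows it: "Laboratory assessments obtained at Days -7 to -1 (Visits 2-3) will not be considered in the determination of enrollment eligibility".
- Protocol 9.3 rests eligibility, in part, on "laboratory assessments obtained at two preceding visits (Visits 1 and 2") and excludes only Visit 3.

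Inclusion criterion 5 (Protocol 4.2 and the Synopsis) sets limits for iPTH, corrected calcium, total 25-hydroxyvitamin D and phosphorus, introduced by "Exhibit after the washout period (if required"). Criterion 4d (users of calcitriol or another 1α-hydroxylated analog) and criterion 4e (vitamin D supplement users at or above 30 ng/mL) require such subjects to "undergo a 4-week washout period and meet inclusion criterion 5".

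**The concern.** Criterion 5 is a post-washout test, but one of the two randomisation rules admits only pre-washout laboratory results. A site working from 5.4 and a site working from 9.3 can therefore treat the same washout subject differently.

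Criterion 5 is not a repeat of Visit 1. Criterion 4 sets no calcium or phosphorus limit. Exclusion 2, which does, ends "5.5 mg/dL if not receiving calcitriol or other" 1α-hydroxylated analog, so it does not cover analog users. Criterion 4a also admits analog users at a lower iPTH than 5a, and 4c exempts supplement users from the 25-hydroxyvitamin D limit.

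Two things are at stake. Corrected calcium and phosphorus are the analytes by which Protocol 6.9 judges safety. And under Protocol 10.8 a deviation from entry criteria may be classed as major; if it is, the PK population definition (Protocol 9.4, SAP 5.4) removes the subject.

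**Working it through.** No sample-size or power figure is involved. The check is which scheduled laboratory draws fall after washout and before randomisation, and which of them each rule allows.

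**Timeline.** SAP 5.6 has no Day 0, so Day −k is k days before Day 1.

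- Visit 1 (Protocol 7.1.1): Days −42 to −36, or Day −70 on the extended schedule. Its labs are 36 to 42 days old at Day 1, or 70.
- Washout (Appendix 1): Days −35 to −8, which is 35 − 8 + 1 = 28 days; or Days −63 to −8, which is 63 − 8 + 1 = 56 days. Visit 1 precedes washout on both schedules.
- Visit 2: Days −7 to −2. Its labs are 2 to 7 days old at Day 1.
- Visit 3: Day −1.
- Visit 4: Day 1. Protocol 7.2.1 places randomisation at the start of the visit, so that day's results come too late.

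**Visible draws after washout and before randomisation.** Protocol 7.1.2 lists a full chemistry panel at Visits 2 and 3, and Table 2 puts corrected calcium and phosphorus in that panel. Section 7.1 lists no visit between Visit 1 and Visit 2. The finding rests on those visit lists, not on blank cells in Appendix 1.

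**What each rule allows for a washout subject.**

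| Criterion 5 limit | Protocol 5.4 / SAP 3.1 | Protocol 9.3 |
|---|---|---|
| 5b corrected calcium | no visible usable draw | Visit 2 |
| 5d phosphorus | no visible usable draw | Visit 2 |
| 5a iPTH | cannot be judged (redaction); any Visit 2–3 draw barred | Visit 2, if drawn |
| 5c total 25-hydroxyvitamin D | week-4 test implied by 4e may serve; any Visit 2–3 draw barred | Visit 2, if drawn |

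**Gap between Visit 1 and criterion 5.** For analog users the iPTH floor is 65 pg/mL in 4a and 85 pg/mL in 5a, a difference of 85 − 65 = 20 pg/mL. A value from 65 to below 85 passes the first and fails the second.

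**Overlap with the PK baseline if Visit 2 decides.** SAP 5.6 averages predose samples and excludes Visit 1, in wording that also mentions Day 1. There are two readings:

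- Only the Day 1 samples at −2 h and 0 h count: Visit 2 weighs 0/2 = 0%.
- Visits 2 and 3 also count, which would explain why Visit 1 has to be excluded: there are 4 calcifediol values, and Visit 2 weighs 1/4 = 25%.

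**The case against.** The strongest reply is that criterion 5 still binds. Every subject must meet the inclusion criteria, 5.4 rests eligibility on Visit 1 labs only in part, and Protocol 7.1.2 schedules inclusion and exclusion review again at Visits 2 and 3. This stands against one tempting inference, that 5.4 licenses randomising washout subjects outside the criterion 5 limits. It does not. But the partial wording appears in 9.3 too and does not lift the separate sentence in 5.4 that bars Visits 2–3. Staff are asked to review criteria at visits whose labs one section forbids them to use.

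A second inference, that no draw exists for any of the four limits, also goes too far. The iPTH and total 25-hydroxyvitamin D rows are redacted. Criterion 4e implies a test at week 4 ("If at the end of 4 weeks of washout, the 25 hydroxyvitamin D level is still" at or above 30 ng/mL), which could settle 5c when washout is not extended. Protocol 3.1 promises weekly samples in the screening and baseline periods, though no visible visit during washout matches it. The single retest in 7.1.1 is for failed Visit 1 values, names no day and is not tied to washout; it neither supplies nor excludes a criterion 5 result.

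Third, the study is descriptive, with no efficacy endpoint and no formal sample size. Calcium and phosphorus are monitored from Day 1, with dose-reduction rules in Protocol 5.3. That tempers the safety argument and the severity, but it does not resolve the contradiction.

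Finally, calling Visit 1 the preceding visit is only loose wording; no weight is placed on it.

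**Conclusion.** The contradiction is explicit, in unredacted text, and would remain whatever the redacted rows contain. Its practical consequence is firm for corrected calcium and phosphorus: under 5.4 and SAP 3.1, a washout subject has no visible scheduled draw by which those post-washout limits may be verified. For iPTH and 25-hydroxyvitamin D the consequence cannot be settled from the public text.

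The practical effect falls mainly on washout subjects, whose number is not given and is not assumed here. Loss from the PK population is possible, not automatic, because it depends on a deviation being classed as major. A reader might infer that the plan permits enrolment outside the limits; the supportable statement is that it takes away the visible means of checking them and gives no rule of precedence. This should be fixed, but it does not undermine the study as a whole.

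**What to change.** Bring Protocol 5.4, Protocol 9.3, SAP 3.1 and both copies of criterion 5 (Synopsis and 4.2) to one rule. For washout subjects, let the already scheduled Visit 2 labs, which 9.3 already admits, decide each criterion 5 limit that no other post-washout draw settles. Name the deciding draw for each of the four limits. If the week-4 test in 4e is to decide 5c, say so. No limit needs to change.

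That is wording in 5 places. One more edit belongs in SAP 5.6: state which samples form the PK baseline and, if Visit 2 is among them, show the calcifediol baseline with and without it. This makes 6 places plus one small display.

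Costs:

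- Some washout subjects will become screen failures.
- Results must be back in the 2 to 7 days between Visit 2 and Day 1; laboratory turnaround is not stated.
- Visit 2 may have to be repeated if washout is extended under 4e.
- If Visit 2 counts in the baseline, a value selected to be below 30 ng/mL also enters that subject's baseline average, so some regression to the mean is possible. Protocol 1.2 treats total 25-hydroxyvitamin D as essentially all calcifediol without significant ergocalciferol use, and a chance deviation at Visit 2 would carry through at one quarter of its size.
- The sponsor must confirm that iPTH and total 25-hydroxyvitamin D are drawn at Visit 2, which redaction hides.

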An Open-Label, Repeated-Dose Safety, Efficacy, Pharmacokinetic and Pharmacodynamic Study of Oral CTAP101 Capsules, IR Calcifediol, High-Dose Cholecalciferol, and Paricalcitol Plus Low-Dose Cholecalciferol in Patients with Secondary Hyperparathyroidism, Stage 3 or 4 Chronic Kidney Disease and Vitamin D Insufficiency.

Study Number:

CTAP101-CL-4001

Study Phase: 4

Objectives:

The objectives of this study are to assess the repeated-dose safety, efficacy, pharmacokinetic (PK) **CCI** profiles of CTAP101 Capsules, IR calcifediol, high-dose cholecalciferol, and paricalcitol plus low-dose cholecalciferol in patients with secondary hyperparathyroidism (SHPT), stage 3 or 4 chronic kidney disease (CKD) and vitamin D insufficiency (VDI).

[figure not shown]
Study Design:

This is a phase 4, multi-center, 4-arm, open-label study to gather comparative data evaluating the safety, efficacy and PK **CCI** profiles for CTAP101 Capsules, IR calcifediol, high-dose cholecalciferol, and paricalcitol plus low-dose cholecalciferol to treat SHPT in male and female subjects aged at least 18 years with stage 3 or 4 CKD and VDI. The study will be conducted at multiple sites within the United States (US). Approximately 160 subjects will be screened to

enroll approximately 80 eligible subjects who will be randomized 1:1:1:1 (approximately 20 per arm, balanced for body weight) to receive 8 weeks of treatment as follows: CTAP101 Capsules at a dose of 60 mcg per day; IR calcifediol at a dose of 266 mcg on Day 1 and Day 29; high-dose cholecalciferol at a dose of 300,000 IU on Day 1 and Day 29; and paricalcitol at a dose of 1 mcg per day (possibly increasing to 2 mcg per day at Day 29) plus low-dose cholecalciferol 800 IU per day. If a significant difference in average weight among subjects by treatment group emerges during the course of the study, subjects may be placed into specific treatment groups rather than randomly assigned, in order to try and achieve more balance in the treatment groups by body weight.

The subjects will be housed in a phase 1 unit for approximately 14 to 26 hours at the beginning of the study and on study Day 29 to provide the blood samples required for a detailed determination of the PK profiles for serum calcifediol (25D₃) **CCI**

CCI

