3.2 Rationale for Study Design

OPKO is developing CTAP101 Capsules for the treatment of SHPT in patients with stage 3 or 4 CKD and VDI. The active ingredient in CTAP101 Capsules is calcifediol, which is formulated as ER capsules for oral administration. The formulation is designed to raise serum total 25-hydroxyvitamin D in a gradual (physiological) manner. Raising blood levels of 25-hydroxyvitamin D too rapidly produces a surge in 1,25-dihydroxyvitamin D production which increases the expression of CYP24A1 in both the kidney and in peripheral target tissues and has significant adverse effects on the expression of other key factors associated with bone and mineral metabolism, including FGF23, CYP27B1, iPTH, calcium and phosphorus [Petkovich et al 2015].

The principal aims of the present study are to compare the safety and efficacy of CTAP101 Capsules, IR calcifediol, high-dose cholecalciferol, and paricalcitol plus low-dose cholecalciferol for up to 8 weeks to treat SHPT in subjects aged 18 years or older with stage 3 or 4 CKD and VDI and to better characterize the repeated-dose PK profiles for serum calcifediol CCI [REDACTED]

[REDACTED]

[REDACTED]

[REDACTED]

[REDACTED]

[REDACTED]

[REDACTED]

[REDACTED]

[REDACTED]

The starting dose of CTAP101 Capsules of 30 mcg/day is the lowest dose approved for marketing in the US. This dose is based on the results from prior repeat-dose, placebo-

controlled, double-blind studies with CTAP101 Capsules in patients with VDI and stage 3-4 CKD. These studies demonstrated that 30 mcg/day of CTAP101 Capsules safely and effectively decreased mean plasma iPTH by clinically meaningful amounts and increased mean serum total 25-hydroxyvitamin D within the currently accepted target range of 30-100 ng/mL.

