3.3 Study Duration

This study is expected to be conducted in approximately 26 weeks from time of initial subject enrollment (first subject consented) to study completion for the last subject (last subject out/last visit complete). Subjects will participate in the study for up to approximately 14 weeks (1 week for screening, 4 weeks for washout (if required), 1 week for BL, and 8 weeks for treatment).

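### Protocol 5.4 and 9.3 can end random allocation on an undefined body-weight trigger, in an open-label trial with no stated concealment of the arm means

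*Protocol*

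**What the plan says.** Protocol 5.4 and 9.3 assign subjects 1:1:1:1 in blocks of 4 at Visit 4. Both then provide for a switch.

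- **Trigger.** Section 5.4 speaks of a significant difference in mean baseline weight. Section 9.3 is worded differently: "In the event that the treatment groups become unbalanced for mean baseline body weight as enrollment progresses". Neither gives a test, a limit in kg, a schedule of looks or a way back to randomisation.
- **Consequence.** In 5.4, "the randomization scheme (described immediately above) will be suspended and subjects will be assigned to a specific treatment group using the following alternative procedure", and 9.3 agrees. The synopsis and Protocol 3.1 are weaker: "subjects may be placed into specific treatment groups rather than randomly assigned".
- **Rule.** Step 2 compares the subject's Visit 1 weight with the mean of everyone treated so far. If it is equal or higher, "then assign the subject to a treatment group (which still has less than 20 subjects) having the lowest mean body weight"; if lower, the subject goes to the open arm with the highest mean.
- **Eligibility laboratory results.** Protocol 5.4: "Laboratory assessments obtained at Visits 2-3 will not be considered in the determination of enrollment eligibility". Protocol 9.3: "Laboratory assessments obtained at Visit 3 will not be considered in the determination of enrollment eligibility", with Visit 2 results counted. SAP 3.1 sides with 5.4.

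The trial is open-label. Protocol 3.1 plans multiple sites; SAP 3.3 allows a single centre and at most three. SAP 3.1 describes the blocks of 4 and omits the alternative procedure. The SAP 7.3 model contains treatment and baseline calcifediol, but not weight.

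**The concern.** Protocol 3.2 states: "The principal aims of the present study are to compare the safety and efficacy", and SAP 7.3 reports between-arm PK differences with 95% confidence intervals and P values. Randomisation is what protects those comparisons from selection.

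Once the switch is made, the next arm follows from the subject's Visit 1 weight and the running means. Anyone who has both can work it out before assignment at the start of Visit 4. Some judgement is still open until then: inclusion and exclusion criteria are reviewed at Visits 2 and 3, and exclusion 7 lets the investigator exclude a subject for a reason thought to make adherence to treatment or follow-up unlikely. If foresight and judgement meet in one person, the arms can come to differ in the kind of subject enrolled.

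**Working it through.** **No planned figure to reproduce.** Protocol 9.2 and SAP 3.2 say that no formal sample size estimation was done. The only arithmetic, 4 × 20 = 80, agrees.

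**1. How often the switch fires by chance.** Simulated with 80 subjects, blocks of 4 and no true weight difference. Weights are normal with SD 20 kg, an assumption that affects only the rows in kg.

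| Reading of the trigger | One look at n=40 | Look after every block (n=8 to 76) |
|---|---|---|
| ANOVA, p<0.05 | 5% | 26% |
| Any pairwise t-test, p<0.05 | 22% | 67% |
| Highest minus lowest mean >5 kg | 95% | 100% |
| >10 kg | 68% | 100% |
| >15 kg | 34% | 98% |

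With ANOVA after every block, a trial that switches places on average 52 of its 80 subjects non-randomly.

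**2. How old the means are when judgement is exercised.** Protocol 3.3 says: "This study is expected to be conducted in approximately 26 weeks from time of initial subject enrollment". A subject takes about 14 weeks with a 4-week washout, or 10 without. Entry is then spread over 26 − 14 = 12 to 26 − 10 = 16 weeks, so 80/16 = 5 to 80/12 = 6.7 starts a week. With the permitted 8-week washout (18 weeks) it could be 80/8 = 10 a week. Visit 3 (Day -1) is thus about one enrolment before assignment, and Visit 2 (from Day -7) about five or more.

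**3. How often the arm is foreseen.** Same weight assumption; the rule starts after 20, 40 or 60 subjects. The alternative is permuted blocks of 4 and 8, stratified by a weight cut, with the best guess from earlier assignments in the stratum. Pure chance is 25%.

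| Information held | Rule (switch at 20/40/60) | Stratified blocks of 4 and 8 |
|---|---|---|
| Current, all subjects | 100% | 48% |
| One enrolment old (about Visit 3) | 49/55/66% | about 42% |
| Five enrolments old (about Visit 2) | about 31/38/48% | about 31% |
| Own site only, 2 sites | 31/32/36% | 28–30% (2–3 sites) |
| Own site only, 3 sites | 28/30/33% | 28–30% (2–3 sites) |

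Under the planned plain blocks of 4, someone who sees every earlier assignment guesses right (1/4 + 1/3 + 1/2 + 1)/4 = 52% of the time.

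**4. Upper bound on the shift.** Suppose the least promising fraction q of subjects foreseen for one arm is never enrolled. For a normal outcome, that arm's mean moves by φ(z_q)/(1 − q) SD, times the share of the arm placed by the rule (60/80 for a switch at 20, 20/80 for a switch at 60).

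- q = 5%: 0.109 × 0.75 = 0.08; × 0.25 = 0.03 SD
- q = 10%: 0.195 × 0.75 = 0.15; × 0.25 = 0.05 SD
- q = 20%: 0.350 × 0.75 = 0.26; × 0.25 = 0.09 SD

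The standard error of a two-arm difference is √(1/20 + 1/20) = 0.32 SD. The bound requires the arm to be foreseen every time and the outcome to be ranked perfectly in advance. If prognosis correlates r with the outcome, the shift is multiplied by r.

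**5. What the rule buys.** Mean range of the four arm mean weights: 2.7–2.8 kg with the rule from n=20, about 5.7 kg with the stratified blocks, about 9.2 kg with plain blocks.

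**The case against.** The study defines no efficacy endpoints, its safety analysis is descriptive and the PK comparison is labelled exploratory. The rule may never be invoked, and it balances weight better than any random scheme considered here. All of that stands and limits the severity.

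Four stronger readings are tempting, and the documents do not support them.

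- *The arm is known throughout screening.* Certainty needs current means. At the criteria reviews the information is already stale, and with several sites an investigator may see only local data.
- *Investigators can exclude whom they like.* Exclusion 7 is tied to expected adherence. Laboratory results come from a central laboratory, and only Protocol 9.3 lets those from Visit 2 count.
- *A bias of 0.26 SD is to be expected.* That figure is a bound. SAP 7.3 also already adjusts for baseline calcifediol, an obvious handle for selection on PK outcomes.
- *Stratified blocks cut predictability from 100% to 48%.* That gap applies only to current, complete information. At Visit 2 after an early switch, or with own-site knowledge, the two schemes are close.

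It can be said that SAP 4 supplies a two-sided 0.05 level, that Protocol 10.9 gives data management and analysis to the sponsor, and that the SAP lists a randomisation schedule. None of these names a weight test, a look schedule or a holder of the arm means. Other SAP models are redacted, so the missing weight term is claimed for 7.3 only.

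A defined trigger with a central holder of the means would close most of the foresight route and keep the tighter balance. It would still leave later subjects placed without any random element.

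**Conclusion.** The point holds as a should-fix. Read literally, Protocol 5.4 and 9.3 replace randomisation by a deterministic rule on a trigger that two sections word differently, and the synopsis and 3.1 make optional what 5.4 and 9.3 make mandatory. Depending on the reading, the chance of a switch with no true imbalance runs from about 5% to nearly 100%. After a switch, the excess predictability over a random weight-stratified scheme is clear with means one enrolment old (49–66% against about 42%). With means five enrolments old it ranges from nothing after an early switch to moderate after a late one (about 31–48% against about 31%).

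The harm is an avoidable opening for selection bias in comparisons that the protocol calls a principal aim. A reader might infer that the trial's conclusions are invalidated; no confirmatory claim exists to be invalidated. The foresight figures rest on normal weights, 20 subjects per arm, the assumed intake and someone actually holding the means. Whether anyone at a site would hold them is not stated. The conflict over Visit 2 laboratory eligibility needs reconciling whatever is decided on allocation.

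**What to change.** 1. In Protocol 5.4 and 9.3, replace the trigger and Steps 1–3 with one central allocation that stays random throughout: permuted blocks of 4 and 8 stratified by a preset Visit 1 weight cut, or minimisation on weight with a random element. State who runs it, and that block sizes and arm means are withheld from sites. Align the synopsis, Protocol 3.1 and SAP 3.1, and reconcile 5.4, 9.3 and SAP 3.1 on Visit 2 laboratory results.
2. Add Visit 1 weight as a covariate in the SAP 7.3 model. Weight plausibly matters for calcifediol: section 5.2 of the product summary in Protocol Appendix 3 says that obese subjects are likely to need larger oral doses.
3. If any subject has already been placed by Steps 1–3, flag those subjects in the listings, change 'randomly assigned' to 'assigned' in Protocol 9.4 and SAP 5.1, 5.3 and 5.4, and add a sensitivity analysis on the randomised subjects only.

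**Cost.** A short protocol amendment and SAP wording, with no extra subjects, visits or measurements. The covariate takes 1 of 80 − 5 = 75 residual degrees of freedom if all 80 subjects are in the model. With the stratified blocks, weight balance is looser than under the rule (about 5.7 kg against 2.7–2.8 kg) though better than with plain blocks, and arm sizes would differ by about 1.5 subjects on average. The covariate handles the remaining imbalance in the PK model only. Some predictability remains at a single site, so withholding block sizes and means is a necessary part of the change.
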